2.4 Determination of sample size

Approximately 300 study participants will be randomly assigned in a 2:1 ratio to the following treatment groups: bimekizumab 160 mg sc (200 study participants) or placebo sc Q4W (100 study participants). The primary efficacy analysis is based on the bimekizumab dose versus placebo for ASAS40 response at Week 16. All sample size and power calculations were done at a significance level of 0.05 in a two-sided test.

All sample size and power calculations were performed using the software nQuery Advisor® 7.0.

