4.2.1.4.1 Non-composite binary endpoints (Modified Composite Estimand)

For non-composite binary endpoints, the MI method will be applied as follows based on raw values:

- Step 1: Any observation after date of discontinuation of study treatment for any reason will be set to missing.
- Step 2: Create a dataset, one for each treatment group, of study participants with observed values and those needing estimation by multiple imputation. For the imputation step, missing values will include non-monotone missing values (ie, intermittent missing values between completed assessments) and monotone missing values (ie, where all study participant data is missing after a given time point).
 - **Step 2a:** First, the intermittent missing values in each dataset will be imputed using the MCMC method with multiple chains, monotone missing data imputing pattern, and non-informative priors for all parameters. Unless specified differently, the first 200 iterations will not be used (the ‘burn-in’ option). A total of 100 sets of imputations will be

performed. The seed used for these imputations will be 2017 and all other multiple imputation procedures described in this SAP will use this same seed as well.

- **Step 2b:** If an imputed value falls outside of the pre-defined range of values for the given variable, the value will be truncated to be within the predefined range of values for the endpoint of interest. For example, the imputed value for BASDAI will be updated to 0 or 10 in the case of an imputed value less than 0 or greater than 10, respectively (see [Table 4–2](#)).

The resulting 100 imputed data sets will have a monotone missing data pattern and will be imputed using a method for monotone missingness:

- **Step 2c:** For monotone missing data, monotone regression will be used to impute missing data. A separate regression model is estimated for each variable with missing values (ie, measurement at each time point). Based on the resulting model, a new regression model is then drawn and is used to impute the missing values for the variable. Since the data set has a monotone missing data pattern, the process is repeated sequentially for variables with missing values. The procedure will be based on the 100 imputed datasets generated from the MCMC procedure and will be performed by Imputation.

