One indicator variable (region1) will be defined as 0 for regions other than North America and 1 for North America. Two more indicator variables (region2 and region3) will be defined similarly replacing North America with Eastern Europe and Western Europe respectively. In the VAR statement of the imputation model, the indicator variables will be ordered as follows: region1 region2 and region3. In the eventuality that two regions required to be pooled due to a low percentage of study participants randomized in one region (see Section 3.8), the indicator variables defined above will be revised accordingly.

- One indicator variable will be defined for the prior TNF α inhibitor exposure stratification variable: will be coded as 1 for yes and 0 for No.

To maintain consistency with the MCMC method for intermittent missing values, these indicator variables will also be used in the monotone regression step for monotone missing values and treated as continuous variables.

- Step 3: For each of the 100 complete imputed data set obtained from Step 2, the binary responder variable will be derived. In practice, the value at the week of interest (eg, Week 16) in the imputed data sets will be used to categorize the study participant as a responder or not. If study participants have a treatment discontinuation due to AE or lack of efficacy, then the endpoint will be changed to “non-response” for all visits after the IE date.
- Step 4:
 - For secondary efficacy endpoints: For each of the datasets obtained in Step 3, the responder rate will be analyzed using a logistic regression model with factors of treatment group, region, and prior TNF α inhibitor exposure as fixed effects. The suitability of including region and prior TNF α inhibitor exposure at Baseline as fixed effects will be assessed using goodness-of-fit tests (Deviance and Pearson’s and Hosmer-Lemeshow) and added if appropriate and allows model convergence.
 - For other efficacy binary endpoints: At each timepoint, the mean proportion of the responders and 95% CIs will be calculated from the imputed datasets using SAS® PROC MIANALYZE.

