Estimates of the adjusted responder rates for each treatment group and the associated standard errors are obtained from the logistic regression in Step 4 on the logit scale and as such are assumed to follow a normal distribution. These estimates will be combined using Rubin’s rules and the combined estimates and associated SEs will be used to construct 95% CIs on the logit scale. The combined estimates and 95% CIs on the logit scale will be back-transformed using the inverse logit link function to obtain the adjusted responder rates (%) and associated 95% CIs.

Some key points to consider relative to the calculation of the odds ratios and corresponding confidence intervals. As the estimates of the odds ratios from the logistic regression model in Step 4 follow a lognormal distribution, a log transformation is needed to normalize these 100 odds ratio estimates since the procedures for combining results from multiple imputed datasets are based on the assumption that the statistics estimated from each imputed dataset are normally distributed. Therefore, the log of the odds ratio estimates from the logistic regression model are used when combining into a single inference (Step 5). Additionally, the standard errors (SE) for the odds ratios are transformed as follows:

$$SE = \frac{\log(UCL) - \log(LCL)}{2Z_{\alpha/2}}$$

where UCL and LCL are the upper and lower confidence limit, respectively, for the CI of the odds ratio from the logistic regression model, and $Z_{\alpha/2}$ is the relevant critical value from the standard normal distribution (1.96 for a 95% CI). The estimates of the log odds ratio for bimekizumab relative to placebo and the corresponding upper and lower confidence limits will be provided. The odds ratio will be then estimated by exponentiating the estimate of the log odds ratio. The odds ratio and the confidence limits of the odds ratio will be estimated as follows:

$$OR = \exp(Log\ odds\ ratio\ estimate)$$

$$LCL = OR * \exp(-SE * Z_{\alpha/2})$$

$$UCL = OR * \exp(SE * Z_{\alpha/2})$$

where OR is the back-transformed estimate of the odds ratio just described, SE is the standard error of the log odds ratio and $Z_{\alpha/2}$ is the relevant critical value from the standard normal distribution (1.96 for a 95% CI). For mean proportion of responders or responder rates, the LCL will be truncated at 0. These calculations will be done such that odds ratios and corresponding CIs are calculated for the odds ratio of bimekizumab versus placebo.

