8.3.2 Analyses of other efficacy endpoints

The efficacy analyses described in this section are not part of the multiplicity-controlled testing procedure described in Section 4.5. Other efficacy endpoints will be analyzed as summarized in Table 4-1.

For the binary variables, the following two estimand structures will be defined:

- Composite Estimand - NRI:

- Population = Study participants enrolled according to the protocol-specified inclusion/exclusion criteria and randomized to IMP
- Study participant-level outcome = The given variable and time point being summarized
- Intercurrent event handling = An intercurrent event is defined as discontinuation of study treatment prior to the time point being summarized. A positive clinical outcome is defined as achieving the given variable at the specified time point and not having an intercurrent event date prior to the time point of interest.
- Population-level summary measure = Unadjusted number and percent of responders
Any missing data that are not preceded by an intercurrent event will be imputed based on NRI as well as any data after an intercurrent event, as described for the primary and secondary binary efficacy endpoints.
- Modified Composite Estimand – MI:
 - Population = Study participants enrolled according to the protocol-specified inclusion/exclusion criteria and randomized to IMP
 - Study participant-level outcome = The given variable and time point being summarized
 - Intercurrent event handling = An intercurrent event is defined as discontinuation of study treatment due to AE or lack of efficacy, prior to the time point of interest. A composite strategy will be implemented in which a positive clinical outcome is defined as achieving the endpoint at the time point of interest and not discontinuing study treatment due to AE or lack of efficacy through the time point of interest.
 - Population-level summary measure = Mean proportion of responders and 95% confidence interval.

An intercurrent event will be acknowledged as an unfavorable outcome for this modified composite estimand in considering study participants with intercurrent events as ‘non-responders’ to the study treatment.

Missing data that are not preceded by an intercurrent event will be imputed by standard MI techniques. Refer to Section 4.2.1.4 for further details.

All binary other efficacy variables will also be summarized using OC approach as defined in Section 8.1.4.6.

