For all these variables, the results based on the NRI will be combined with the ones obtained on OC and from the MI analysis in one single table.

In addition, a line plot by treatment group will be produced over time for some of the endpoints, that are part of the sequential testing procedure, based on NRI results, including the following binary variables: ASAS40 responder rate, ASAS40 responder rate in the TNF alpha inhibitor naïve study participants, ASAS20 responder rate, ASAS5/6 responder rate, ASAS-PR responder rate, and ASDAS-MI responder rate.

Continuous other efficacy variables that are components of the primary endpoint will be analyzed using the reference-based MI estimand and procedure described in Section 8.1.4.3.

For the continuous and categorical other efficacy variables (not including change from Baseline in WPAI-SHP, ASspiMRI-a (Berlin modification) score, and SPARCC score, and EQ-5D-3L Utility scores), the following estimand structure will be defined:

- Hypothetical Estimand (Section 4.2.1.7) – MI:
 - Population = Study participants enrolled according to the protocol-specified inclusion/exclusion criteria and randomized to IMP
 - Study participant-level outcome = The given variable and time point being summarized
 - Intercurrent event handling = An intercurrent event is defined as discontinuation of study treatment prior to the time point being summarized. This estimand targets the treatment difference in a scenario where the intercurrent event does not occur, such that outcomes for study participants without an intercurrent event are as observed at the given time point, and outcomes for study participants with an intercurrent event are treated as though they had completed the randomized study treatment through the time point being summarized
 - Population-level summary measure = Unadjusted mean.

The same imputation strategy for handling missing data as the one used for the secondary continuous efficacy endpoints as described in Section 8.2.2 will be implemented. Missing data for ASDAS status endpoint will also be imputed using MI, and the imputation will be done on the components of ASDAS-CRP prior to calculating ASDAS-CRP and categorizing ASDAS status. The mean proportion of responders in the multiply imputed data sets (with the associated 95% CI based on SE) will be displayed for each ASDAS category.

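### The SE-based 95% intervals for multiply imputed responder proportions and ASDAS categories under-cover when rates are below about 5%, and print as 0 to 0 when there are no responders

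*SAP*

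**What the plan says.** SAP Section 8.3.2 sets the modified composite MI summary for other binary variables as "Population-level summary measure = Mean proportion of responders and 95% confidence interval". For ASDAS status it displays, per category, "The mean proportion of responders in the multiply imputed data sets (with the associated 95% CI based on SE").

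The calculation is in Section 4.2.1.4.1, Step 4, for other binary endpoints: "the mean proportion of the responders and 95% CIs will be calculated from the imputed datasets using SAS® PROC MIANALYZE". No model and no transformation is mentioned. Section 4.2.1.5 adds "For mean proportion of responders or responder rates, the LCL will be truncated at 0".

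The rates from the logistic models are handled differently. Section 4.2.1.5 pools them on the logit scale and states "The combined estimates and 95% CIs on the logit scale will be back-transformed using the inverse logit link function". That route serves the primary endpoint's MI analysis and the secondary binary endpoints. The SAP gives no rule for an arm with no responders.

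**The concern.** Direct pooling of a proportion and its SE, a limit based on the SE, and a lower limit that needs cutting at 0 all point to a symmetric interval on the probability scale. A back-transformed logit limit cannot fall below 0, so on that scale the truncation rule would have nothing to do.

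Symmetric intervals of this kind are poor for small proportions. When the observed count is low by chance, the estimated SE is low too, so the upper limit falls short of the true rate. At a count of zero the SE is zero.

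Such cells are plausible here. ASAS-PR is also listed among the other efficacy variables (Section 2.2.1.3), so it enters the by-visit tables. Early visits and ASDAS inactive disease on placebo may be rarer still, but the SAP gives no rates for them. In Section 8.3.2 the NRI summary of these variables is a number and percentage only, so the MI interval is the only interval that section specifies for them. At stake is how precise those descriptive rates appear to be.

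**Working it through.** **Inputs.** Arm sizes are from Section 2.4: "bimekizumab 160 mg sc (200 study participants) or placebo sc Q4W (100 study participants"). Section 4.2.1.4.1 sets 100 imputations. Section 2.4.2 gives planning rates at Week 16: ASAS-PR 17% versus 3.3%, and placebo 5% in the ASAS5/6 paragraph. Rates of 1% and 2% are assumptions, standing in for early visits and rare ASDAS states.

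**The plan's own figure.** The SAP states no coverage beyond the nominal 95%. The planning figure that carries the 3.3% rate is the ASAS-PR power of 94%. Recomputed with the continuity-corrected chi-square test at 200 versus 100, it is 94.2%, so those inputs are read correctly.

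**Method.** With complete data, Rubin's total variance is the within-imputation variance, so the interval for x responders out of n is p̂ ± 1.96 × √(p̂(1 − p̂)/n), with p̂ = x/n and the lower limit cut at 0. Exact coverage at a true rate p is the sum of the binomial probabilities of every x whose interval contains p.

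**Worked case, n = 100, p = 3.3%.**
- x = 0: interval 0 to 0, misses.
- x = 1: 0.01 ± 1.96 × √(0.01 × 0.99/100) = −1.0% to 2.95%, shown as 0 to 2.95%, misses.
- x = 2 to 8: contain 3.3%.
- x ≥ 9: lower limit above 3.3%, misses.

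P(0) + P(1) = 3.5% + 11.9% = 15.4%, and P(x ≥ 9) = 0.6%. Coverage is 100 − 15.4 − 0.6 = 84.0%. A balanced interval would miss about 2.5% on each side.

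**Exact coverage, n = 100.**

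| True rate | SE-based | Wilson |
|---|---|---|
| 1% (assumed) | 63.3% | 92.1% |
| 2% (assumed) | 86.6% | 94.9% |
| 3.3% (SAP) | 84.0% | 95.2% |
| 5% (SAP) | 87.7% | 96.6% |
| 10% | 93.2% | 93.6% |
| 15% | 93.3% | 93.3% |

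Coverage moves in a sawtooth: 94.5% at 2.9%, 80.2% at 3.0%, 90.6% at 4.0%. The average over 3 to 6% is about 89%, which is a fairer summary than any single point. With n = 200, coverage is 89.2% at 3.3%, 92.6% at 5% and 94.9% at 17%.

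**Effect of missing data.** A simulation of the Rubin-pooled interval used n = 100, 100 imputations, an assumed 5% or 10% missing completely at random, and a simple beta-binomial imputation in place of the SAP's component-level imputation. Coverage was 83 to 92% at 3.3%, 91 to 94% at 5%, 83 to 84% at 2% and 61 to 65% at 1%. Missing data therefore softens the shortfall at 3.3 to 5% but not at 1 to 2%.

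**Zero responders.** If no imputed data set has a responder, the within- and between-imputation variances are both 0 and the interval is 0 to 0. With complete data, P(0 of 100) = (1 − p)^100, which is 3.5% at 3.3%, 13.3% at 2% and 36.6% at 1%. The Wilson upper limit at 0/100 is 1.96²/(100 + 1.96²) = 3.84/103.84 = 3.7%.

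**The case against.** Much of the case for leaving the text alone is sound.

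- **These are single-arm exploratory summaries.** They lie outside the multiplicity procedure, and the binary line plots use NRI. This stands, and it limits the consequence.
- **The low rates that the SAP documents belong to key secondary endpoints at Week 16.** Their inferential MI analysis already uses logit-scale pooling. This also stands; the criticised interval reaches those endpoints only in the by-visit tables. A reader might infer that one Week 16 rate is given two contradictory intervals. That is not so: one is a covariate-adjusted model rate and the other a mean proportion.
- **The coverage figures depend on the rate chosen and on ignoring missing data.** This is partly right, hence the 3 to 6% average and the simulation. Neither restores 95%.
- **The scale is inferred.** The truncation sentence also names responder rates, which could include the logit-scale rates, so it may be a blanket safeguard. Even so, direct pooling and an SE-based limit point the same way, and no other interval is given.
- **A zero count is visible beside the interval.** True, but a 95% interval of 0 to 0 still says something false.

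A reader might also infer that truncation causes the under-coverage. It does not: a true rate is never below 0, so cutting the limit there loses nothing. The symmetric form is the cause.

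**Conclusion.** The point holds for the by-visit MI proportions of other binary variables and for the ASDAS categories. Where an arm has about 100 participants and the rate is below about 5%, the nominal 95% interval covers about 89% on average over 3 to 6% and 84.0% at 3.3%. It covers 87% and 63% at assumed rates of 2% and 1%. The misses come almost entirely from upper limits that are too low. A 0 to 0 interval has complete-data probability 3.5% at 3.3% and 37% at an assumed 1%. It requires that none of the 100 imputed data sets contains a responder, so it will not follow every zero observed count. From about 10% upward the shortfall is small.

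The harm is overstated precision in descriptive cells: chiefly placebo up to Week 16 (placebo participants then switch to bimekizumab), early visits and rare ASDAS states. It is tempting to conclude that the arms will look more separated than the data support. The documents do not show this, because no between-arm comparison uses these intervals. The primary and key secondary tests, the odds ratios and the adjusted rates are unaffected.

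The conclusion rests on the inferred probability scale, the planned arm sizes, and the assumed rates wherever the SAP gives none.

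**What to change.** In Section 4.2.1.4.1 Step 4 and in Section 8.3.2, state that the 95% CI for a mean proportion is the Wilson interval for multiply imputed data, built from the MI point estimate and the total variance. One way to write it: let Ū be the within-imputation variance, B the between-imputation variance and M = 100. Set r = (1 + 1/M)B/Ū and use the Wilson formula with n replaced by n/(1 + r) and Rubin's critical value. Set r = 0 when Ū = 0, so that 0/100 gives 0 to 3.7%. Then drop the truncation sentence in Section 4.2.1.5 for these proportions, since the Wilson lower limit cannot fall below 0.

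Extending the logit pooling of Section 4.2.1.5 would not be enough alone, because the logit is undefined in any imputed data set with no responders.

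The cost is a few lines of SAP text and a small macro. Intervals for rare states become slightly wider or shift upward: for 3/100 with complete data, from 0 to 6.3% to 1.0 to 8.5%. No point estimate, test or imputation changes.

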8.3.3 Additional statistical analysis of selected other efficacy variables

Although statistical testing is not planned for other efficacy variables per protocol, statistical testing and inferential statistics are of interest for selected endpoints. As these tests are not part of the multiplicity-controlled procedure, the associated p-values are considered nominal and should not be used for inference. Similarly as described in Section 8.2.3, statistical tests and calculation of inferential statistics will be performed for the following selected other efficacy endpoints:

- ASAS40 at Week 1, Week 2, Week 4, Week 8, Week 12
- ASAS40 in the TNF alpha inhibitor-naïve study participants at Week 1, Week 2, Week 4, Week 8, Week 12
- ASAS20 at Week 1, Week 2, Week 4, Week 8, Week 12
- PGADA at Week 1, Week 2, Week 4, Week 8, Week 12, Week 16
- Total spinal pain at Week 1, Week 2, Week 4, Week 8, Week 12, Week 16
- Nocturnal spinal pain at Week 1, Week 2, Week 4, Week 8, Week 12
- BASFI at Week 1, Week 2, Week 4, Week 8, Week 12
- Mean BASDAI Q5 and Q6 score at Week 1, Week 2, Week 4, Week 8, Week 12, Week 16
- BASDAI at Week 1, Week 2, Week 4, Week 8, Week 12,
- BASDAI50 at Week 1, Week 2, Week 4, Week 8, Week 12, Week 16
- CRP at Week 1, Week 2, Week 4, Week 8, Week 12, Week 16
- ASDAS-CRP at Week 16
- MASES at Week 16
- Enthesitis free state at Week 16
- TJC at Week 16
- SJC at Week 16
- FACIT-Fatigue at Week 16
- WPAI at Week 16
- ASspiMRI at Week 16
- SPARCC at Week 16

The same models as described in Section 8.2.3 will be run, and results will be presented in one single table together with the results for secondary endpoints.

In addition, the Week 16 results from the primary analysis for the primary endpoint ASAS40, and key secondary endpoints in the hierarchy (ASAS20, BASDAI, BASFI, nocturnal spinal pain) will also be included in this table.

9 PHARMACOKINETICS AND IMMUNOGENICITY

9.1 Pharmacokinetics

Only study participants treated with bimekizumab will be included in the PK analyses. For the study participants randomized to placebo group, Baseline will be the Week 16 pre-dose sample.

9.1.1 Definition of ADAb Sample Status (positive, negative, missing)

ADAb sample results will be provided as “Positive Screen” (PS) or “Negative Screen” (NS). For samples presenting anti-BKZ antibody levels that are PS, further confirmatory assay will be performed, and the result of which will be reported as either “Positive Immunodepletion” (PI) or “Negative Immunodepletion” (NI).

ADAb status for each sample will be derived as following:

- Sample values that are either NS, or PS and NI and where the BKZ concentration is less than the validated ADAb assay drug tolerance limit (200 µg/mL) will be defined as ADAb negative.
- Sample values that are either NS, or PS and NI and where the BKZ concentration exceeds the validated ADAb assay drug tolerance limit will be defined as inconclusive.
- Sample values that are PS and PI will be defined as ADAb positive (regardless of availability of a titer value).
- Missing or non-evaluable samples will be defined as missing.

PI samples will be titrated, and the ADAb titer (reciprocal dilution factor including MRD) reported. The PI samples will also be subject to a neutralizing assay to evaluate whether the anti-BKZ antibody neutralizes target binding of bimekizumab (IL17AA or IL17FF or both) in-vitro (as described in the next section).

